**APPENDIX III – GRADING OF ADVERSE EVENTS**

The severity of adverse events will be graded according to the U.S. Department of Health and Human Services, National Institutes of Health, National Institute of Allergy and Infectious Diseases, Division of AIDS. Division of AIDS (DAIDS) Table for Grading the Severity of Adult and Pediatric Adverse Events, Corrected Version 2.1. [July 2017]. Available at:

<https://rsc.niaid.nih.gov/sites/default/files/daidsgradingcorrectedv21.pdf>

## APPENDIX IV – GRADING OF VITAL SIGNS

Use the following criteria to grade vital signs:

Grading Scale*	Grade 1 (mild)	Grade 2 (moderate)	Grade 3 (severe)	Grade 4 (potentially life-threatening)
Temperature (C°) (F°)	38.0-38.4 100.4-101.1	38.5-38.9 101.2-102.0	39.0-40.0 102.1-104.0	>40.0 >104
Tachycardia (beats/min)	101-115	116-130	>130	ER visit or hospitalization for arrhythmia
Bradycardia (beats/min)	50-54	45-49	<45	ER visit or hospitalization for arrhythmia
Hypertension systolic (mmHg)	141-150	151-155	>155	ER visit or hospitalization for malignant hypertension
Hypertension diastolic (mmHg)	91-95	96-100	>100	ER visit or hospitalization for malignant hypertension
Hypotension systolic (mmHg)	85-89	80-84	<80	ER visit or hospitalization for hypotensive shock
Respiratory Rate (breaths/min)	17-20	21-25	>25	Intubation
SPO 2 (%)	92 - <95	90 - <92	85 - <90	<85 or ER visit or hospitalization for hypoxia

\* Taken from Toxicity Grading Scale for Healthy Adult and Adolescent Volunteers Enrolled in Preventive Vaccine Clinical Trials {CBER, 2007}, except SPO2.

Document Approvals  
Approved Date: 21 Apr 2021

Approval Task Verdict: Approve	Director, Clinical Development
	21-Apr-2021 15:23:11 GMT+0000

Approval Task Verdict: Approve	
	21-Apr-2021 15:24:22 GMT+0000

Approval Task Verdict: Approve	tor, Clinical Research
	21-Apr-2021 15:37:29 GMT+0000

## Change History Table

Version	Summary of Major Change(s) and Impact	Revision Date
Version 1.0	First approved version of SAP	28/May/2021
Version 1.1	Amendment for change of ULOQ of binding immunoassay in SAP Section 8.5.1, due to update in PK Analytical Testing Plan	01/Dec/2021

[COVID-HIGIV]  
[EBS-CVH-003]

## List of Abbreviations and Definition of Terms

**Table 1: List of Abbreviations and Definitions of Terms**

Abbreviation	Definition
AE	Adverse Event
AESI	Adverse Event of Special Interest
AUC	Area Under the Curve
AU	Alliance unit(s)
BMI	Body Mass Index
CI	Confidence Interval
cm	Centimeter(s)
COVID-19	Coronavirus disease 2019
COVID-HIGIV	Anti-SARS-CoV-2 Immunoglobulin Intravenous (Human)
CSR	Clinical Study Report
CV	Coefficient of Variation
d	Day(s)
ECG	Electrocardiogram
eCRF	Electronic Case Report Form
EDC	Electronic Data Capture
ELISA	Enzyme-Linked Immunosorbent Assay
EWV	Early Withdrawal Visit
g	Gram(s)
GMC	Geometric Mean Concentration
GMT	Geometric Mean Titer
GMR	Geometric Mean Ratio
h	Hour(s)
ICF	Informed Consent Form
ID	Identification, as in Subject Identification (number)
IgG	Immunoglobulin G (gamma globulin)
IgM	Immunoglobulin M
IP	Investigational Product
IV	Intravenous
LLOQ	Lower Limit of Quantification
LOD	Limit of Detection
MedDRA	Medical Dictionary for Regulatory Activities
mL	Millilitre(s)
NP	Nasopharyngeal
PE	Physical Examination

[COVID-HIGIV]  
[EBS-CVH-003]

PI	Principal Investigator
PK	Pharmacokinetics
SAE	Serious Adverse Event
SAP	Statistical Analysis Plan
SD	Standard Deviation
SMC	Safety Monitoring Committee
SOC	System Organ Class
TLF	Tables, Listings and Figures
ULOQ	Upper Limit of Quantification
US	United States
WHO	World Health Organization

[COVID-HIGIV]  
[EBS-CVH-003]

## 1 INTRODUCTION

This Statistical Analysis Plan (SAP) is based on Protocol EBS.CVH.003 “A Phase 1, Double-blind, Randomized, Placebo-controlled Study to Evaluate Safety and Pharmacokinetics of Anti-SARS-CoV-2 Immunoglobulin Intravenous (Human) Investigational Product (COVID-HIGIV) Administered as a Single Dose or a Repeat Dose Regimen to Healthy Adults” (Version 4.0, 21Apr2021). This document specifies details of the definitions of the derived variables, analysis methods, assumptions and data handling conventions. The document is accompanied by mock-up tables, listings, and figures (TLF Specification). Some further details on the calculation of derived variables will be provided as programmer’s notes in the TLF shells. The TLF shells serve only as a guide for programming the final TLF. They are working documents and can be updated as needed.

## 2 PROTOCOL SUMMARY

### 2.1 Study Objectives

#### 2.1.1 Primary Objectives

- To evaluate PK of three dose levels of COVID-HIGIV administered IV as a single dose to healthy adults.
- To evaluate safety of three dose levels of COVID-HIGIV administered as a single dose to healthy adults.

### 2.2 Study Design and Conduct

This study is a Phase 1, single-center, double-blind, randomized, placebo-controlled design to evaluate three dose levels of COVID-HIGIV for safety and PK in healthy adults.

Subjects will be enrolled into the study consisting of healthy adult non-pregnant females and males (SARS-CoV-2 negative). In total, 28 subjects are planned for the study ([Table 1](#) below).

**Table 1**

Study Arm	No. of Subjects	Treatment*	Study Arm Label
1	8	COVID-HIGIV Dosage 1	COVID-HIGIV 100 mg/kg
2	8	COVID-HIGIV Dosage 2	COVID-HIGIV 200 mg/kg
3	8	COVID-HIGIV Dosage 3	COVID-HIGIV 400 mg/kg
4	4	Placebo (saline)	Placebo

\* Note: COVID-HIGIV Dosage 1-3 are prepared by IP volume (mL) based on subject body weight (kg).

COVID-HIGIV protein concentration  $\approx$  100 mg/mL, the dosages in study arm label are in the unit of mg/kg.

Dosage 1: prepared by COVID-HIGIV volume ( $\approx$ 1 mL/kg), with a maximum of 100 mL, labeled as 100 mg/kg,

Dosage 2: prepared by COVID-HIGIV volume ( $\approx$ 2 mL/kg), with a maximum of 200 mL, labeled as 200 mg/kg.

Dosage 3: prepared by COVID-HIGIV volume ( $\approx$ 4 mL/kg), with a maximum of 400 mL, labeled as 400 mg/kg.

[COVID-HIGIV]  
[EBS-CVH-003]

Eligible subjects will be randomized 2:2:2:1 to four study treatment arms to receive a single IV infusion of COVID-HIGIV at one of three dose levels or saline placebo.

The enrollment/dosing of the first seven subjects in the study will be staggered wherein no more than three subjects will be dosed on the same day (to be dosed at least one hour apart). Principal Investigator (PI) and the Sponsor's Medical Monitor (MM) will review blinded data (up to 24 hours after end of IV infusion) before proceeding with dosing subsequent set of remaining subjects for the stagger. Available safety (blinded) data will be reviewed by Study Monitoring Committee (SMC) (consisting of at least three independent external members) after seven subjects from Cohort A have completed at least 72 hours of safety follow-up. If unblinding of the safety data is required, closed session by the SMC will be held. An overall decision by the SMC will be made whether to proceed with full randomization and dosing of the remaining study subjects.

Following dosing, each subject will stay overnight in the inpatient unit for close observation; each dosed subject will be discharged from the inpatient unit once all assessments at 24 hours post-dosing timepoint (i.e., Day 2) are completed.

The SMC will perform overall ongoing review of safety data during the study. Study enrollment and administration of study treatments may be temporarily paused by the SMC for safety review if any of the following occur after study product administration and during the study's follow-up period:

- One or more serious adverse event(s) [SAE(s)]
- Three or more of the same adverse events (AEs) classified as grade 3 severity.
- Five or more of the same AEs classified as grade 2 severity.

Subjects will be followed for safety and PK assessments up to 84 days post-dosing. If any subject tests positive for SARS-CoV-2 via a point-of-care RT-PCR test of nasopharyngeal (NP) samples during the study follow-up period, they may be withdrawn from the study, but allow for telemedicine follow-up plus home healthcare visits. They will be assessed for COVID-19 symptoms using modified WHO ordinal score ([Appendix V](#)) in the Early Withdrawal visit (EW).

The final statistical analyses will be conducted after all subjects complete the study.

## 2.3 Randomization and Blinding

This is a double-blinded, placebo-controlled, single site study.

### 2.3.1 Methods of Randomization

Subjects will be randomized into four treatment arms, with a randomization ratio of 2:2:2:1, and a block size of seven (two subjects at COVID-HIGIV dosage level 1, two subjects at COVID-HIGIV dosage level 2, two subjects at COVID-HIGIV dosage level 3, and one placebo subject).

[COVID-HIGIV]  
[EBS-CVH-003]

The first seven subjects will be randomized and dosed in a staggered manner, with dosing at least one hour apart, and not exceeding three subjects on the same day.

### 2.3.2 Randomization Errors

A *mis-randomization* is defined as a subject receiving a study treatment other than the one assigned by randomization.

*Stratification error* happens when a subject is randomized based on incorrect stratification information at baseline or if a subject is mistakenly put into a wrong block. In either case, the subject uses up one position in the assigned block and randomization can continue.

Both mis-randomization and stratification error are reported as protocol deviations.

### 2.3.3 Blinding and Unblinding

Randomization list is generated by a third-party statistician (Axiom RTSM team) and not provided to the sponsor until unblinding.

At the site, the designated unblinded pharmacist will receive the treatment and dosage assignment from the Randomization and Trial Supply (RTSM) module and prepare the infusion bags accordingly, all infusion bags are of 400 mL volume and masked for blinding. Details on the randomization procedures are provided in the Pharmacy Manual (*Version 1.0, 03Dec2020*).

In addition, designated personnel at the bioanalytical laboratory assigned to perform PK sample testing will be unblinded due to nature of test; however, the personnel at the bioanalytical laboratory will not have access to clinical data and will not disseminate the link between bioanalytical laboratory results and the actual subject ID until database lock. PK statistician will analyze PK result by dummy subject ID and nominal timepoints of PK sampling during the study. Other personnel involved in the conduct of the clinical study will remain blinded until database lock and final unblinding. Details on the blind maintenance will be provided in the Blind Maintenance Plan (*Version 1.0, 15Jan2021*).

The final study unblinding is planned after all subjects complete the Day 85 visit (i.e., 84 days post-dosing).

Per current CDC guidelines, subjects who received immunoglobulin products should avoid vaccination for up to 90 days afterwards. The local standard of care in COVID-19 pandemic changed during the trial such that all adults >16 years of age became eligible to receive the COVID-19 vaccine in New York State. As a result, subjects who received placebo will be informed of their treatment assignment after all subjects have completed the Day 29 so that they may follow current COVID-19 vaccine recommendations. Immediate unblinding of treatment assignment to receive COVID-19 vaccination is also allowed after the Day 29 visit on a case-by-case basis based on PI judgement and will be considered as medical emergency unblinding. Unblinded Placebo recipients will be kept in the study for safety follow-up, but no PK samples will be drawn. Unblinded COVID-HIGIV recipients will continue follow up as per the protocol.

[COVID-HIGIV]  
[EBS-CVH-003]

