Study Arm	No. of Subjects	Dosing Schedule – Day 1														
1	8	COVID-HIGIV dosage 1*														
2	8	COVID-HIGIV dosage 2**														
3	8	COVID-HIGIV dosage 3***														
4	4	Placebo (saline)														

	
unit once all assessments at 24 hours post-dosing timepoint (i.e., Day 2) are completed.
 
The SMC will perform overall ongoing review of safety data during the study. Study enrollment and administration of study treatments may be temporarily paused by the SMC for safety review if any of the following occur after study product administration and during the study's follow-up period:
 
 
• One or more serious adverse event(s) [SAE(s)].
 
• Three or more of the same adverse events (AEs) classified as grade 3 severity.
 
• Five or more of the same AEs classified as grade 2 severity.
 
 
Note: refer to Section 8.2 for AE severity grading.
 
Placebo recipients may be unblinded upon request after all subjects have completed Day 29 to allow them to follow current COVID-19 vaccination guidelines.
 
Subjects will be followed up for safety and PK up to 84 days post-administration of a single dose.
 
If any subjects become positive for SARS-CoV-2 during the study follow-up period, they will be assessed using modified WHO ordinal score (see Appendix I – Modified WHO Ordinal Scale) until they complete their last follow-up visit (via telemedicine).

Inclusion Criteria	
The following criteria will be used for inclusion into the study:
 
 
1. Able and willing to provide written informed consent (voluntarily signed by the subject) prior to performing study procedures.
 
2. Females and males 18-60 years of age, inclusive.
 
3. Have a body mass index (BMI) less than or equal to 35.0 kg/m^2.
 
4. Women who are either: 
 
A) Not of childbearing potential: either surgically sterile (at least six weeks post bilateral tubal ligation, bilateral oophorectomy or hysterectomy); or post-menopausal (defined as <math>\geq</math>50 years of age with a history of <math>\geq</math>12 months without menses prior to randomization in the absence of other pathologic or physiologic causes, following cessation of exogenous sex-hormonal treatment); OR
 
 
 

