## Clinical Study Protocol EBS-CVH-003

Version 4.0, 21 Apr 2021

Access to information in electronic data capture (EDC) system will be blinded using role-based permissions. Randomization group and study treatment dispensing data will be provided to Emergent after database lock and unblinding. Dosing data will be reconciled with the randomized treatment group for each subject by the unblinded monitor, and any deviations will be reported in the Clinical Study Report (CSR).

Upon request, subjects who received placebo will be informed of their treatment assignment after all subjects have completed the Day 29 to follow current COVID-19 vaccine recommendations. Placebo recipients will be kept in the study for safety follow-up, but no PK samples will be drawn.

While this is a double-blind study, an unscheduled unblinding may occur at any point after the infusion. Details on the reasons for unblinding and the associated unblinding procedures will be described in the Pharmacy Manual. In an event of unblinding, Emergent must be notified.

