#### 3.2 Safety Endpoints

The following primary safety endpoints will be evaluated:

- Adverse Events (AEs) within 72 hours post-dosing.
- AEs leading to discontinuation or temporary suspension of infusion.
- AEs and Serious Adverse Events (SAEs) up to 84 days post-administration of a single COVID-HIGIV dose.

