### **9.2.2 AEs Related to Study Treatment**

Relationship of AEs to the study treatment will be assessed by the PI or designee, and reviewed by the Sponsor, using terms and scales “Unrelated”, “Possibly related”, “Probably related”, and “Definitely related”. If the relationship between the AE and the study treatment is determined to be “Possibly” or “Probably” or “Definitely” related, the event will be considered as related to the study treatment.

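### SAP 2.3.3 keeps personnel blinded to database lock, yet it informs all placebo recipients after Day 29, so late adverse-event judgments cannot be assumed blinded for active versus placebo

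*SAP*

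**What the plan says.** SAP 2.3.3 exempts the site pharmacist and the bioanalytical laboratory from the blind and then states: "Other personnel involved in the conduct of the clinical study will remain blinded until database lock and final unblinding". It adds: "The final study unblinding is planned after all subjects complete the Day 85 visit".

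The same section, citing vaccine eligibility, says that "subjects who received placebo will be informed of their treatment assignment after all subjects have completed the Day 29". No request is required. It makes two further provisions:

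- Informed placebo recipients stay in safety follow-up but give no more PK samples. Unblinded active recipients continue as before.
- After the Day 29 visit, a subject may be unblinded at once for vaccination, case by case, on the investigator's judgment. This is classed as medical emergency unblinding.

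The protocol is narrower. Section 3.5 says: "Upon request, subjects who received placebo will be informed of their treatment assignment after all subjects have completed the Day 29". The synopsis (Protocol Design) says: "Placebo recipients may be unblinded upon request after all subjects have completed Day 29".

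On safety, SAP 3.2 lists as a primary endpoint "AEs and Serious Adverse Events (SAEs) up to 84 days post-administration of a single COVID-HIGIV dose". SAP 9.2.2 says: "Relationship of AEs to the study treatment will be assessed by the PI or designee", with sponsor review. The AE summaries in SAP 9.2.1 include related AEs by arm; their only time split is at 72 hours.

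**The concern.** There are two kinds of treatment, active and placebo. If every placebo recipient is told, everyone else is known to be active, whether or not anyone is vaccinated. The statement that personnel stay blinded to database lock then fails, in substance, for active versus placebo during part of follow-up, and SAP 2.3.3 does not say so.

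What is at stake is the late part of the 84-day endpoint. Relatedness is a judgment. An assessor who knows that a subject had saline has little reason to call an event related, while one who knows that a subject had product can do so more readily. Subjects' own reporting can shift in the same way. The planned tables would pool events from before and after disclosure, with nothing to show that the comparison changed character.

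**Working it through.** **Arm sizes.** SAP 2.3.1 gives a 2:2:2:1 ratio in blocks of seven; SAP 4 gives 28 subjects. 28 / (2+2+2+1) = 4 blocks, hence 8, 8, 8 and 4, which reproduces the stated arms. Active subjects: 28 − 4 = 24.

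**What disclosure reveals.** If k placebo recipients are known, the chance that a subject not known to be placebo is in fact on placebo is (4 − k)/(28 − k), when block membership is unknown:

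| k | Chance of placebo | Certain active if blocks can be inferred (6k) |
|---|---|---|
| 0 | 4/28 = 14.3% | 0 |
| 1 | 3/27 = 11.1% | 6 |
| 2 | 2/26 = 7.7% | 12 |
| 3 | 1/25 = 4.0% | 18 |
| 4 | 0/24 = 0% | 24 |

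Under the SAP wording k reaches 4 and all 24 are identified. Under the protocol wording k depends on requests, so full identification is possible but not automatic. Dose level is not revealed in either case.

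**How much follow-up is exposed.** The general trigger is completion of Day 29 by all subjects, taken here as the nominal Day 29 (28 days after dosing) of the last subject dosed. A subject dosed s days before the last one has max(0, 84 − 28 − s) = max(0, 56 − s) open days.

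- Last subject (s = 0): 56 of 84 days = 66.7%.
- Any subject dosed 56 or more days earlier: 0 days.

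The enrollment span is not given. Assuming, for illustration only, evenly spaced dosing of 28 subjects, the average exposed share is:

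| Span (days) | Average open share of 84 days |
|---|---|
| 0 | 66.7% |
| 14 | 58.3% |
| 28 | 50.0% |
| 56 | 33.3% |
| 84 | 22.6% (18 of 28 subjects have any open follow-up) |

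These figures cover the general trigger only. If the case-by-case route runs from a subject's own Day 29 visit, that subject can have up to 84 − 28 = 56 open days even if dosed early.

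**Whether the assessor learns the arm.** There are two routes.

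- *Case by case: direct.* SAP 2.3.3 classes this as medical emergency unblinding. Protocol 8.10 has the investigator carry out emergency unblinding personally in the randomization system. Protocol 8.3 makes the investigator responsible for causality.
- *General disclosure: inferred.* The SAP says that subjects are told, not assessors. But PK draws stop for informed placebo recipients only, at visits run by site or home healthcare staff (Protocol 6.3.2). Concomitant medications are recorded at the same visits, so a vaccination would show. Neither document names a separate blinded AE assessor.

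**Endpoints affected.** AEs within 72 hours, and AEs leading to stopping or suspending the infusion, precede any Day 29 disclosure and are untouched. Only later AEs and SAEs within the 84-day endpoint, and their relatedness, are exposed.

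**The case against.** The strongest reply is that this is a deliberate, explained exception for vaccine access, stated openly in both documents, and that its effect is small. Two of the three primary safety endpoints are untouched. Protocol 1.2.2 expects the common reactions during infusion or within hours of it. No hypothesis is tested. All AEs are tabulated regardless of causality, the Medical Monitor judges SAE causality independently (Protocol 8.3), and the sponsor, which reviews relatedness, does not hold the randomization list. The AE listing is sorted by start date and time, so a before-and-after reading is already possible by hand.

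Most of this stands, and it limits the matter to how descriptive data are read. It does not remove it. Independent causality review covers SAEs only, a listing is not a planned summary, and the exception is never carried into the sentence that promises blinding to lock.

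A reader might also infer more than the documents support:

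- *All 24 active subjects lose two thirds of their blinded follow-up.* All 24 become identifiable, but 67% is the last subject's figure under the general trigger; early enrollees may have none.
- *The first disclosure ends the blind for everyone.* One known placebo recipient still leaves an 11.1% chance of placebo for each other subject when blocks are unknown.
- *Late judgments will certainly be unblinded.* On the general route this is an inference. The Blind Maintenance Plan is not available and could hold a safeguard, although the cited version (15 Jan 2021) predates protocol version 4.0 (21 Apr 2021).
- *The study report will conceal the disclosure.* Nothing says so.

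**Conclusion.** The point holds in a bounded form. SAP 2.3.3 claims a blind to database lock that its own disclosure rule does not preserve for active versus placebo. Once all four placebo recipients are informed, the remaining 24 are identifiable as active, and later AE reporting and relatedness judgments cannot be assumed blinded.

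The exposed share of the 84-day window is between 0 and 56/84 (67%) per subject under the general trigger. This assumes nominal visit days and that the last subject dosed sets the trigger. The average cannot be fixed without enrollment dates, and individual unblinding could come earlier. Assessor unblinding is direct on the case-by-case route and inferred on the general one.

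The SAP and protocol also contradict each other on whether disclosure requires a request. The consequence lies in interpreting late descriptive safety data; no test, PK result or early safety endpoint is at risk. It should be corrected because the remedy uses data already collected.

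**What to change.** 1. In SAP 2.3.3 and Protocol 3.5, write the exception into the statement on blinding to database lock. Say that the active-versus-placebo blind is not assured after the general placebo disclosure, or after a subject's own unblinding if that is earlier.
2. In SAP 9.2.1 and 9.2.2, present AEs and related AEs by arm, by onset before versus on or after the earlier of the subject's own unblinding date and the general disclosure date. Rest any blinded placebo-controlled statement on the earlier period. Protocol 8.10 already requires the date to be recorded for safety-related or accidental unblinding; record it for the general disclosure too. If the request wording is kept, define the general date; the date on which disclosure became available is the cautious choice.
3. Reconcile the on-request condition in the protocol (synopsis and Section 3.5) with the unconditional wording in SAP 2.3.3.

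Having the pharmacist disclose without telling the assessor would not work. It conflicts with the investigator's personal duty in Protocol 8.10 on the case-by-case route, and it cannot hide the stopped PK draws.

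The cost is a SAP amendment, one extra split of existing tables and, for the protocol wording, an amendment with ethics approval (Protocol 12.7). The downside is a shorter blinded comparison and very sparse cells with four placebo subjects. The decision to disclose for vaccination is not questioned here.

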#### **Adverse Events (AE)/Serious Adverse Events (SAE):**

AE will be coded to system organ class (SOC) and preferred term using the Medical Dictionary for Regulatory Activities (MedDRA), using the most current version at the time of coding. AEs will be defined as events beginning after study treatment administration that were not present prior to study treatment administration or those that were present prior to study treatment administration and subsequently worsened in severity.

- AE within 72 hours post-dosing will be summarized by SOC and preferred term.

- AEs and SAEs within 84 days post-dosing will be summarized in the same manner as described above in the first bullet.
- Discontinuation or temporary suspension of infusion will be summarized by treatment group.

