## 9.2 Adverse Events

AEs will be coded to system organ class (SOC) and preferred term (PT) according to the Medical Dictionary for Regulatory Activities (MedDRA).

AEs reported from the signing of the ICF until immediately before the first dose of IP on Day 1, will be in generally recorded as Medical History, unless it is study procedure associated, which may be considered as non-treatment-emergent AE. A treatment emergent adverse event (TEAE) is defined as an AE that was not present prior to administration of the first dose of study medication and any study procedures and present after the first dose or procedure, or if it represents the exacerbation of an event that was present prior to the first dose or procedure.

Only TEAEs will be included in the summaries described below and 'AE' will refer to TEAE, unless otherwise specified. For AE summaries, an AE occurs on the first dosing date but without onset time will be counted as treatment emergent. AEs with missing start dates, but with stop dates overlapping into the treatment period will also be counted as treatment emergent.

A subject data listing of all AEs (including treatment-emergent AEs (TEAEs) and non-TEAEs) sorted by analysis group, subject ID and AE start date/time will be provided.

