### 9.2.1 Overall Summary of AEs

The following list of AEs summaries will be provided by SOC and PT in tabulate format. The events will be sorted in descending frequency of subjects in the "Total" column for SOC, then PT, unless otherwise specified.

- All AEs
- All AEs occur within 72 hours post-dosing (from the start of infusion to 72 hours post the end of infusion)
- All AEs by maximum severity
- AEs related to study treatment (COVID-HIGIV or placebo)
- AEs of Grade 3 and higher severity
- AEs of Grade 3 and higher severity and related to study treatment
- AEs by analysis group sorted by PT in descending frequency among all COVID-HIGIV treated subjects AE Severity

The Investigator is responsible for the assessment of the severity of an AE using the following criteria:

- Mild (Grade 1): awareness of a sign or symptom but subject can tolerate.
- Moderate (Grade 2): discomfort enough to cause interference with normal daily activity.
- Severe (Grade 3): resulting in an inability to do work or do usual daily activity.

[COVID-HIGIV]  
[EBS-CVH-003]

- Potentially Life-Threatening (Grade 4): emergency room visit or hospitalization.
- Death (Grade 5)

Subjects having the same AE more than once will be counted once for each PT and once within each SOC at the maximum severity. If the severity is missing for one or more of the occurrences, the maximum severity of the remaining occurrences will be used.

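### The all-cause Day-84 AE tables do not separate events after COVID-19 vaccination, so vaccine reactions can enter mainly through the four-subject placebo column

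*SAP*

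**What the plan says.** **Unblinding.** SAP 2.3.3 explains that adults in New York State became eligible for COVID-19 vaccine during the trial. Placebo recipients are therefore told their assignment once every subject has completed Day 29. Earlier unblinding in order to be vaccinated is allowed case by case after the Day 29 visit, and that route is not limited to placebo. For placebo, "Unblinded Placebo recipients will be kept in the study for safety follow-up, but no PK samples will be drawn". For the product arms, the section cites guidance that "subjects who received immunoglobulin products should avoid vaccination for up to 90 days afterwards".

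**Endpoint and tables.** One of the three primary safety endpoints in SAP 3.2 is AEs and SAEs "up to 84 days post-administration of a single COVID-HIGIV dose". Protocol 9.6.2 states: "AEs and SAEs within 84 days post-dosing will be summarized in the same manner as described above in the first bullet". SAP 9.2.1 lists tables of all AEs, AEs by maximum severity and "AEs of Grade 3 and higher severity", plus related-AE versions. SAP 9.3.2 tabulates all SAEs. The only AE table restricted in time covers the first 72 hours.

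**Related text that does not agree.** Protocol 3.5 makes unblinding conditional: "Upon request, subjects who received placebo will be informed of their treatment assignment after all subjects have completed the Day 29". The synopsis agrees: "Placebo recipients may be unblinded upon request after all subjects have completed Day 29". SAP 2.3.3 attaches no such condition. Exclusion criterion 1 (synopsis and Protocol 4.2) still names use of a SARS-CoV-2 vaccine during follow-up.

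**The concern.** The plan creates an event that can itself cause AEs, expects it mainly in one arm, and then counts all AEs in that arm as if the event had not occurred. Placebo is the only control for the Day-84 endpoint. If vaccine reactions are added to background events in that column, and the product columns largely lack them, the product looks relatively safer than it should. The SAP gives SARS-CoV-2 infection its own summaries (9.6 and 9.7) but says nothing on vaccination.

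**Working it through.** **Inputs**
- N = 28, allocated 2:2:2:1 in blocks of seven (SAP 2.3.1 and 4).
- AEs are captured from infusion to the Day 85 visit (Protocol 8).
- The Safety Set is all dosed subjects (SAP 5.2).
- Day 29 visit at 28±2 days; Day 85 visit at 84±3 days (Protocol 6.3.2 and 6.3.3).

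**1. Planned arm sizes.** 28 × 2/7 = 8 per dose level and 28 × 1/7 = 4 placebo, as stated. That is four blocks with one placebo subject in each. The plan has no power or alpha figure to reproduce.

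**2. Can a vaccine reaction reach the tables?**
- The Safety Set has no stop at vaccination.
- The treatment-emergent definition in SAP 9.2 has no stop either.
- No table in 9.2.1 or 9.3.2 is split after 72 hours, and SAP 6.8 plans no subgroups.
- The 72-hour AE endpoint and the infusion-interruption endpoint close long before Day 29, so they are unaffected.

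**3. Weight of one subject whose only AE is a vaccine reaction**
- Placebo column: 1/4 = 25 points.
- One dose arm: 1/8 = 12.5 points.
- Pooled COVID-HIGIV: 1/24 = 4.2 points.
- Total column: 1/28 = 3.6 points.
- Equivalence: 1/4 = 2/8 = 6/24.

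**4. Time at risk after unblinding.** Take a placebo subject dosed *d* days before the last subject. By the general route (all subjects past Day 29), the days left are at least 81 − (30 + *d*) and at most 87 − (26 + *d*), floored at 0.

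| *d* (days) | Days left |
|---|---|
| 0 | 51 to 61 |
| 14 | 37 to 47 |
| 28 | 23 to 33 |
| 56 | 0 to 5 |

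The 61-day figure is a ceiling. The first seven subjects must complete 72 hours and committee review before the other 21 are dosed. The first-block placebo subject therefore has *d* of at least 3, and by this route at most 87 − (26 + 3) = 58 days. Case-by-case unblinding straight after the Day 29 visit leaves 51 to 61 days whatever *d* is.

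**5. Precision without any contamination.** The exact (Clopper-Pearson) 95% interval for 1/4 is 0.6% to 80.6%.

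**6. Illustration on assumed rates only.** Let *k* of the four placebo subjects be vaccinated, *pv* be the chance of a reportable reaction and *p0* the background any-AE risk. The expected rise in placebo any-AE incidence is (*k*/4) × (1 − *p0*) × *pv*. Assume *p0* = 0.01 to 0.30 and *pv* = 0.3 to 0.8.
- *k* = 1: from 0.25 × 0.70 × 0.3 = 5.25 points to 0.25 × 0.99 × 0.8 = 19.8 points.
- *k* = 2: 10.5 to 39.6 points.

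None of these rates is in the documents, so the range only restates the assumptions. The effect on the Grade 3 or higher and SAE tables would be smaller and cannot be sized.

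**The case against.** The case against concerns consequence, and much of it stands.

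- **Nothing is tested.** No hypothesis is planned, and a four-subject column is very imprecise even when clean. No test result can be wrong.
- **Partial protection exists.** The related-AE tables leave out reactions judged unrelated to study treatment. The protection is incomplete: the all-cause tables remain, and after unblinding the causality call may be made with the assignment known.
- **Dated records are planned.** The AE listing will be "sorted by analysis group, subject ID and AE start date/time will be provided". SAP 6.5.1 has date rules for concomitant medications and keeps unimputed values in listings, and SAP 9.5.3 displays these medications by group. Matching two listings for four subjects is easy if vaccines are entered as medications. The case report form and table shells are not available, so that cannot be settled here. No SAP text links a vaccination date to AE onset.
- **Exclusion criterion 1 points the other way.** Depending on how it is reconciled with SAP 2.3.3, a vaccinated subject might appear as a protocol deviation. That would not remove the AEs from the Safety Set.

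A reader might infer that vaccine reactions will occur only in placebo. The documents do not support that. The 90-day statement is cited guidance, and SAP 2.3.3 provides for COVID-HIGIV recipients who are unblinded. Setting the 25 points against the 1 to 15% incidence in Protocol 1.2.2 is also tempting, but that range describes reactions to immunoglobulin products, not all-cause AEs.

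**Conclusion.** The gap in the SAP text is real and minor. The plan anticipates vaccination mainly among four placebo subjects and does not separate later AEs in the all-cause Day-84 tables. The size that rests on the documents alone is 25 points in the placebo column per subject whose only AE is a vaccine reaction, against 12.5 in a dose arm. The likely direction flatters the product.

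That vaccination falls mainly in placebo rests on the cited guidance being followed. A reader might go further and conclude that the placebo rate will be inflated, or that the safety comparison is biased by a known amount. The documents do not support either: they give no uptake and no reaction rates, and exposed time may be near zero for early enrollees. The expected size is unknown. The harm is a potentially misleading control column in one of three primary safety endpoints of a descriptive study.

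**What to change.** In SAP 9.2:
- Keep the Day-84 tables as the primary-endpoint display.
- Add a supplementary AE/SAE table from dosing to the Day 29 visit. Its windows are nearly equal in all arms (26 to 30 days) and it precedes the planned unblinding.
- Flag, in tables and listings, any AE that starts after a first COVID-19 vaccine dose, in any arm.
- Report by arm the number vaccinated and the follow-up days before and after vaccination.
- Optionally, add a Day-84 version without post-vaccination AEs. Follow-up would then be unequal, with as few as 26 placebo days against 81 to 87 active days, so it must be read beside those days.

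Record vaccination dates with concomitant medications. Two sets of passages must be reconciled: the request condition in the protocol synopsis and 3.5 with the unconditional wording of SAP 2.3.3; and exclusion criterion 1 with the text on unblinding for vaccination.

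The cost is SAP wording, a listing flag and one or two extra tables. If nothing changes, a manual check remains possible, provided vaccination dates were recorded.
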